Division of Internal Medicine
Department of Vascular Diseases

[name]
[name]
T [name]
F [name]
E [contact]
W www.kclj.si

Date: January 26, 2019

Study Protocol and Statistical Analysis Plan

Arterial Function and Atherosclerosis in Patients With JAK2 V167F Positive Essential Thrombocythemia

Principal Investigator: [name], PhD,
Professor of Medicine,
Head, Department of Vascular Diseases

Funding: Project No. TP20180038, financed by the Fund for Tertiary Research and Development of the University Medical Centre Ljubljana

1. Overview and Aim of the Study

We will study patients with JAK2 V617F positive essential thrombocythemia (ET) without clinically apparent atherosclerotic vascular disease in comparison to age-and sex-matched, apparently healthy control subjects and measure changes in vascular function and morphology at baseline and after a 4-year observation period. In addition, the JAK2 V617F allele burden, i.e., the percentage of mutated alleles in leukocytes, will be determined and correlated with vascular function and morphology. The study protocol has been approved by the Committee for Medical Ethics of the Republic of Slovenia, approval number: 0120-428/2017/4.

Our aim is to test (a) whether changes in vascular function and morphology in a 4 year observation period differ between patients with JAK2 V617F positive ET in comparison with control subjects, and whether (b) the JAK2 V617F allele burden correlates with vascular function and morphology.

2. Patients and Control Subjects

Patients with JAK2 V617F positive ET have been selected from the database of the Department of Hematology of the University Medical Centre Ljubljana, Slovenia, after having given their informed consent. Only patients without a personal history of clinically manifest atherosclerotic vascular disease (myocardial infarction, angina pectoris, peripheral arterial disease, aortic disease, transient ischemic attack or ischemic stroke) were eligible. The control group has been selected among apparently healthy employees of the University Medical Centre Ljubljana and their relatives. The groups have been matched for age and sex distribution and classical risk factors for cardiovascular disease. Forty patients (14 male and 26 female) with JAK2 V617F positive ET without clinically apparent cardiovascular disease were enrolled in the study in 2014 - 2015 for the first examination and 36 (12 male and 24 female) of them are expected to participate also in 2018-19. Forty two control subjects (16 male and 26 female) participated in the first examination in 2014-2015 and at least 38 (14 male and 24 female) subjects are expected to participate in the second examination.

Inclusion criteria for patients are: clinically confirmed ET with genetically confirmed JAK2 V617F mutation, age above 18 years, absence of clinically suspected or overt atherosclerotic vascular disease. For the control subjects, the inclusion criteria are being apparently healthy, matching the patients in age and sex, age above 18 years, and absence of clinically suspected or overt atherosclerotic vascular disease.

Exclusion criteria for both groups are: clinically suspected or overt atherosclerotic vascular disease, chronic kidney disease stage 3 and above, known cancer, chronic inflammatory disease, autoimmune disease, and pregnancy.

All subjects will be examined twice, the first time in 2014 - 2015 and the second time in 2018 – 2019. All participants will have signed the informed consent form before enrolment. The subjects will complete a structured questionnaire about personal and family medical history, risk factors for cardiovascular disease and their medication. They will be physically examined and will donate blood samples for laboratory tests. Ultrasound examination of the extracranial carotid arteries will be done, and echo-tracking of the common carotid arterial wall will be used to assess the β-stiffness index and to estimate the pulse wave velocity. EndoPat plethysmography will be used to assess the endothelial function via the reactive hyperemia response of the digital arteries. Coronary artery calcium scanning will be performed to evaluate the extent of coronary artery calcification.

3. Baseline Measurements

Every participant will be examined physically, including measurements of height, weight, waist circumference, systolic and diastolic blood pressure. Blood will be taken for laboratory analyses - electrolytes, complete blood cell count, serum lipids, liver function tests, urea, creatinine, inflammatory markers and DNA

isolation for measurement of JAK V617F allele burden. A structured questionnaire about family history of cardiovascular diseases, personal medical history, smoking status and medications will be completed. The 10-year risk of coronary heart disease (CHD) and general cardiovascular disease (CVD) will be calculated using the Framingham risk equation.

4. Vascular Imaging

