Differences between subjects with ET and control subjects at the first and second examination will be tested by the chi-square test for discrete variables, for normally distributed continuous variables by the paired Student's t-test for independent samples, and for non-normally distributed continuous variables by the Mann-Whitney test for independent samples. P-values of < 0.05 will be considered significant with a correction for multiple comparisons.

Changes in vascular function and morphology in the 4-year observation period will be compared between the two groups by the log rank test. P-values of < 0.05 will be considered significant.

The association between the parameters of vascular function / morphology and the JAK2 V617F allele burden will be assessed by the Pearson correlation coefficient.

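### The only planned test of 4-year change between the non-randomised groups (aim (a)) uses none of the collected risk factors, so residual imbalance among those examined twice could be read as an ET effect

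*Combined protocol and SAP*

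**What the plan says.** Section 1 sets aim (a) as a comparison of 4-year change between ET patients and controls. Section 2 draws patients from a haematology database and controls from healthy hospital staff and their relatives, and applies the same exclusions to both. On comparability it states: "The groups have been matched for age and sex distribution and classical risk factors for cardiovascular disease". The control inclusion criteria in the same section repeat age and sex only. Of the 40 patients first examined, "36 (12 male and 24 female) of them are expected to participate also in 2018-19"; of the 42 controls, "at least 38 (14 male and 24 female) subjects are expected to participate in the second examination".

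Sections 2 and 3 collect smoking status, lipids, blood pressure and medication, and Section 3 adds a summary score: "The 10-year risk of coronary heart disease (CHD) and general cardiovascular disease (CVD) will be calculated using the Framingham risk equation".

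Section 7 gives one test for change: "Changes in vascular function and morphology in the 4-year observation period will be compared between the two groups by the log rank test". It names no covariate or stratum. Separately, "Differences between subjects with ET and control subjects at the first and second examination will be tested by the chi-square test for discrete variables", with t-tests or Mann-Whitney tests for continuous variables, and "P-values of < 0.05 will be considered significant with a correction for multiple comparisons". No regression, stratified or sensitivity analysis appears anywhere in Section 7.

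**The concern.** The groups were not randomised, so a difference in change can come from ET or from anything else that differs between patients and staff or relatives. Analysing change removes stable differences in level. It does not remove differences in factors that affect how fast the arteries change, such as smoking or lipids.

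Matching reduces this problem, but the plan gives no tolerances or balance measure, and the matching was of those enrolled, not of those who return. The risk factors needed to deal with what is left are collected, yet enter no test of change. A reader of a crude difference will ask whether risk factors explain it, and the plan has no answer fixed in advance. Covariates picked after the data are seen would be open to selection.

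**Working it through.** The plan states no power, effect size or SD, so there is no figure of its own to reproduce. The calculation below shows how much an imbalance could matter. It uses a comparison of mean change as a stand-in, because Section 7 defines no event or time variable for the log rank test.

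**Inputs from Section 2:** 36 patients (12 male) and 38 controls (14 male) at the second examination; 40 (14 male) and 42 (16 male) at the first.

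**Assumptions:** imbalance of 0.2 to 0.3 SD in one covariate; correlation r of 0.1 to 0.5 between that covariate and change; two-sided 5% test; no ET effect.

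**Step 1, precision.** In SD units of change, SE = √(1/36 + 1/38) = 0.2326, with 74 − 2 = 72 degrees of freedom.

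**Step 2, bias.** Bias = imbalance × r. The smallest is 0.2 × 0.1 = 0.02 SD and the largest is 0.3 × 0.5 = 0.15 SD.

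**Step 3, rejection rate of the crude test** (noncentral t, noncentrality = bias / 0.2326):

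| Imbalance | r = 0.1 | 0.2 | 0.3 | 0.4 | 0.5 |
|---|---|---|---|---|---|
| 0.2 SD | 5.1% | 5.3% | 5.7% | 6.3% | 7.1% |
| 0.3 SD | 5.2% | 5.7% | 6.7% | 8.0% | 9.8% |

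**Step 4, the one factor with data.** Males: 12/36 = 33.3% and 14/38 = 36.8%. Standardised difference = (0.368 − 0.333) / √[(0.333 × 0.667 + 0.368 × 0.632) / 2] = 0.035 / 0.477 = 0.07. Over the same range of r this gives 5.0% to 5.3%, which is negligible.

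**Step 5, whether the planned group tests would reveal an imbalance.** At 36 versus 38, a two-sided 5% test has power 13.6% for a true 0.2 SD difference and 24.7% for 0.3 SD. The plan does not name its multiplicity correction. If it were Bonferroni over 10 tests (level 0.005, assumed), power would be 2.5% and 6.0%. A non-significant result would not show balance.

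**Step 6, what adjustment costs and gains.** Simulation at 36 versus 38 with a 0.3 SD imbalance in one covariate plus four inert ones (20,000 runs):

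| r | Crude rejection | Adjusted rejection | Crude SE | Adjusted SE |
|---|---|---|---|---|
| 0.1 | 5.2% | 4.9% | 0.232 | 0.242 |
| 0.3 | 6.5% | 4.8% | 0.232 | 0.232 |
| 0.5 | 9.4% | 4.9% | 0.232 | 0.210 |

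The adjusted rate is near 5% by construction, since the simulated confounder is in the model. The SE is about 4% wider at r = 0.1 and about 9% narrower at r = 0.5. Residual degrees of freedom fall from 72 to 67 with five covariates, or 66 with six. The sixth widens the SE by roughly a further 1% (√(67/66) = 1.008).

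**The case against.** The strongest case is that confounding is already handled by design. The groups are stated to be matched on classical risk factors as well as age and sex, the exclusions are shared, one ultrasonographer examines everyone at both visits, and change removes stable differences in level. Nothing in the documents shows that an imbalance remains, and the 0.2 to 0.3 SD is assumed. All of this stands. It limits the point to residual imbalance that cannot be ruled out.

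Adjustment is also not free. In a simulation of the same setup (4,000 runs), root-mean-square error at r = 0.1 rose with adjustment, from 0.233 to 0.241 at 0.2 SD imbalance and from 0.237 to 0.246 at 0.3 SD. At r = 0.2 there was no gain. Adjustment helped from about r = 0.3. The documents give no correlation. This too stands, and is why the crude result should stay in the report.

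Three stronger readings are tempting and should not be drawn.

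- **Unequal follow-up time.** Section 2 says "All subjects will be examined twice, the first time in 2014 - 2015 and the second time in 2018" to 2019. The calendar extremes allow 24 months (end of 2015 to start of 2018) to 72 months (start of 2014 to end of 2019). Bias would need the mean interval to differ between groups. Both groups share the same windows, and nothing suggests they were scheduled differently.
- **Loss to follow-up has unbalanced the groups.** Expected losses are 4 of 40 and 4 of 42, and in each group two men and two women. Sex does not settle other factors, but the figures give no sign of differential loss.
- **The 5.1% to 9.8% range is the error rate of the planned test.** It is not. It applies to a comparison of means. Whether log rank suits measures taken at two examinations is a separate question.

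**Conclusion.** The point holds in limited form. Aim (a) is a non-randomised comparison whose only planned test of change takes no account of the collected risk factors. Matching of those enrolled does not guarantee balance among those examined twice, and the planned group tests are too weak to confirm it.

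The actual bias cannot be computed from the documents. Under the stated assumptions it runs from negligible (5.1% to 5.7% rejection at r = 0.1 to 0.2) to material (7.1% to 9.8% at r = 0.5). The documents do not show that the groups are in fact imbalanced. An adjusted estimate should be added because it is cheap and answers a predictable question in advance, not because the crude result is known to be wrong. Confidence is medium. Aim (b) is outside this point.

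**What to change.** In Section 7, prespecify for aim (a) an adjusted between-group difference in change with a 95% confidence interval, reported beside the crude result, whatever is decided about log rank.

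- **Intima-media thickness, β-stiffness, PWV, RHI and AI:** linear model of change on group, age, sex, smoking, one lipid measure and months between examinations. Section 3 says only serum lipids, so name the measure now. Months enter as a precision covariate, without implying that intervals differ between groups.
- **Plaque score and Agatston score:** the same covariates in one model type fixed in advance, for example ordinal.
- **Systolic pressure:** add the baseline value for every outcome except β-stiffness and PWV, which Section 4.1 calculates from blood pressure.
- **Sensitivity analyses:** (1) add the baseline value of the measure; (2) replace the separate risk factors with the Framingham CVD risk. Read the second with care for β-stiffness and PWV if the equation's inputs, which the documents do not list, include blood pressure.
- **Balance table:** risk factors and medication by group among those examined twice, judged by standardised differences, not P-values. Medication is tabulated and not adjusted for, because treatment given for ET would go with group.

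The cost is SAP wording and some extra analysis, with no new measurements. If the covariates predict change only weakly, the SE is about 4% wider with five covariates and about 5% with six. The Framingham version with months leaves 70 degrees of freedom and widens it by about 2% (0.232 to 0.237). Unmeasured differences between patients and staff or relatives remain.

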4.1. Carotid Artery Ultrasound Examination

For examination of the extracranial carotid arteries an ultrasound machine Aloka Prosound a7 (Hitachi Aloka Medical, Ltd., Japan) will be used with a linear vascular probe working at a frequency of 5-13 MHz. The common, internal and external carotid arteries on both sides will be examined. At each examination, the measurements will be done twice and their average values will be calculated. The ultrasound examination will be done by the same ultrasonographer at both visits of all participants.

The intima-media thickness will be measured 2 cm proximal to the bulb of common carotid artery on both sides. Screening of the extracranial carotid arteries for atherosclerotic plaques will be performed, with a plaque definition of a focal lesion, exceeding the intima-media thickness for at least 50% or reaching an absolute thickness of at least 1.5 mm in two orthogonal projections. Scoring of atherosclerotic plaques is done according to the methodology from the Rotterdam Study. The presence of at least one plaque in each segment of the extracranial carotid arterial bed, (divided into the common carotid artery and the bulb, the internal carotid artery and the external carotid artery) on either sides is scored 1 point. Thus, the carotid plaque score ranges from 0 (absence of plaques) to 6 (plaques present in all segments on both sides).

Echo-tracking of the common carotid artery will be used to assess arterial stiffness expressed by the β -stiffness index and the pulse wave velocity. Measurements will be done at the common carotid artery 2 cm proximal to the bulb on both sides. The β -stiffness index will be calculated as: $\beta = \ln(P_{\max} / P_{\min}) / [(D_{\max} - D_{\min}) / D_{\min}]$, where P_{\max} = the systolic blood pressure, P_{\min} = the diastolic pressure; D_{\max} = the maximum arterial diameter and D_{\min} = the minimal arterial diameter. Pulse wave velocity (PWV) will be calculated as: $PWV = \sqrt{((\beta \times P_{\min}) / 2\rho)}; \rho = 1050 \text{ kg/m}^3$.

4.2. Measurement of the Coronary Artery Calcium Burden

The calcium burden of coronary arteries will be measured with a Biograph M 128-row PET-CT scanner (Siemens, Erlangen, Germany). A non-contrast protocol with sequential prospective ECG triggering will be used. Post-processing will be done on the Syngo Leonardo workstation. The coronary calcium burden will be expressed as the Agatston score.

5. Assessment of Endothelial Function of the Digital Arteries

Endothelial function of the digital arteries will be measured by digital plethysmography with EndoPat 2000, Itamar Medical REF, Caesarea, Israel, Software Version 3.3.x and expressed as the Reactive Hyperaemia Index (RHI) and the Augmentation Index (AI). Changes in arterial tone are elicited by creating a downstream hyperemic response induced by a standard 5-minute occlusion of the brachial artery (using a blood pressure cuff, inflated to 60 mmHg above the arterial blood pressure). When the cuff is released, the surge of blood flow causes endothelium-dependent flow mediated dilatation (FMD) which is manifested as reactive hyperemia. A post-

occlusion to pre-occlusion ratio is calculated by EndoPAT software and the and A) are determined. The results are normalized to a heart rate of 75/min.

6. Measurement of the JAK2 V617F/G1849T Allele Burden

The ipsogen JAK2 MutaQuant Kit, Qiagen (ZDA) (Ref: No. 673523) will be used for the detection and quantification of JAK2 V617F/G1849T allele in genomic DNA extracted from peripheral blood of patients and of control subjects. JAK2 V617F allele burden will be calculated and expressed as a percentage of JAK2 V617F mutated alleles throughout the whole JAK2 record.

7. Statistical Analysis

All sets of data will be tested for normality of distribution using the normal-quintile plot, calculating the correlation coefficient and checking it for the critical value that would warrant rejection of normal distribution with an α -error probability of 0.05.

Normally distributed data will be presented as mean and standard deviation, while non-normally distributed data will be presented as median and range between the 1st and 3rd quartile.

Differences between subjects with ET and control subjects at the first and second examination will be tested by the chi-square test for discrete variables, for normally distributed continuous variables by the paired Student's t-test for independent samples, and for non-normally distributed continuous variables by the Mann-Whitney test for independent samples. P-values of < 0.05 will be considered significant with a correction for multiple comparisons.

Changes in vascular function and morphology in the 4-year observation period will be compared between the two groups by the log rank test. P-values of < 0.05 will be considered significant.

The association between the parameters of vascular function / morphology and the JAK2 V617F allele burden will be assessed by the Pearson correlation coefficient.

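### The groups were matched on age, sex and risk factors, but the tests at each examination use none of these, so they are likely to be conservative and to lose power, though they stay valid

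*Combined protocol and SAP*

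**What the plan says.** The overview (section 1) describes patients studied "in comparison to age-and sex-matched, apparently healthy control subjects". Section 2 is more specific: "The groups have been matched for age and sex distribution and classical risk factors for cardiovascular disease". This is matching of distributions. No pairs are described, and the group sizes differ: "Forty patients (14 male and 26 female) with JAK2 V617F positive ET" against "Forty two control subjects (16 male and 26 female) participated in the first examination". For the second examination, "36 (12 male and 24 female) of them are expected to participate also in 2018-19" and, among controls, "at least 38 (14 male and 24 female) subjects are expected to participate in the second examination".

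Section 7 plans the cross-sectional comparison as follows: "Differences between subjects with ET and control subjects at the first and second examination will be tested by" "the chi-square test for discrete variables", a Student's t-test for normally distributed measures and a Mann-Whitney test for the rest. The sentence calls the t-test both paired and for independent samples. Significance is at 0.05 with an unnamed correction for multiple comparisons. No part of section 7 adjusts for, or stratifies by, age, sex or any risk factor.

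The two aims in section 1 are the group difference in 4-year change and the correlation with allele burden. The comparisons at each examination are planned, but they are neither of these.

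**The concern.** Matching two groups on a factor that predicts the outcome largely removes that factor from the difference in group means. A test that ignores the factor still counts its variance as noise, so the standard error in the test is larger than the real sampling variation of the difference. The test then rejects too rarely under the null hypothesis. A regression containing the factor uses only the residual variance.

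The group sizes were fixed by the 2014–2015 enrolment and can only fall by the second examination, so the analysis is the main remaining way to gain precision. With a low-powered test, a non-significant ET–control comparison could be read as no difference when an adjusted analysis of the same data would have shown one.

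**Working it through.** The documents give no sample-size calculation, effect size or SD, so there is no planned figure to reproduce.

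**Inputs from section 2.** 40 against 42 at the first examination; 36 against 38 expected at the second. The sex counts add up (14+26=40, 16+26=42, 12+24=36, 14+24=38). Male share is 14/40 = 35.0% against 16/42 = 38.1%, then 12/36 = 33.3% against 14/38 = 36.8%: close balance on sex, not exact.

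**Assumptions (not in the documents).** Age and sex explain a share R² of the outcome variance, from 0 to 0.5. The true difference is 0.5 SD. Tests are two-sided at 0.05 without the multiplicity correction.

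**Formulas, outcome SD = 1.**
- Standard error used by the two-sample test: SE = √(1/n₁ + 1/n₂). This is √(1/40 + 1/42) = 0.2209 and √(1/36 + 1/38) = 0.2326.
- Actual SD of the difference: s·SE, with s = √(1 − R² + k·R²). Here k is the share of the chance variance in covariate imbalance that the matching leaves: k = 0 is exact balance, k = 0.25 is imbalance halved, k = 1 is no matching.
- Standard-error inflation at exact balance: 1/√(1 − R²).
- True type I error: 2·[1 − Φ(1.96/s)]. Example, R² = 0.3: at k = 0, s = √0.7 = 0.837 and the result is 1.9%; at k = 0.25, s = √0.775 = 0.880 and it is 2.6%.
- Unadjusted power (k = 0): Φ[(0.5 − 1.96·SE)/(s·SE)]. Adjusted power: Φ[0.5/(√(1 − R²)·SE) − 1.96].

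| R² | SE inflation | Type I error, exact balance | Type I error, imbalance halved | Power 40/42, unadjusted → adjusted | Power 36/38, unadjusted → adjusted |
|---|---|---|---|---|---|
| 0 | 1.00 | 5.0% | 5.0% | 61.9% → 61.9% | 57.5% → 57.5% |
| 0.1 | 1.05 | 3.9% | 4.2% | 62.5% → 66.5% | 57.9% → 62.0% |
| 0.3 | 1.20 | 1.9% | 2.6% | 64.1% → 77.2% | 59.0% → 72.9% |
| 0.5 | 1.41 | 0.6% | 1.3% | 66.6% → 89.3% | 60.6% → 86.0% |

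These are normal approximations. With the t distribution (78 degrees of freedom) adjusted power at 40/42 is about one point lower: 61%, 65%, 76% and 88%.

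**Simulation check, R² = 0.3, 40 against 42.** With exact balance, the t-test and the Mann-Whitney test each reject in about 2% of runs under the null; the regression rejects in about 5%. Power is about 63% for the t-test against about 76% for the regression. With half the chance imbalance left, null rejection is about 2.5–3%.

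**Which part is due to the matching.** With no matching (k = 1), s = 1 and the unadjusted type I error returns to 5%. Simulated power at R² = 0.3 is then about 62% unadjusted against 76% adjusted, nearly the same gap as with matching.

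**Would pairing help?** When the groups are paired in arbitrary order, a paired t-test at R² = 0.3 has 58% power. That is no better than the two-sample test, and two controls are dropped.

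**The case against.** The strongest reply is that the planned two-sample tests are valid: a conservative test does not produce false findings, and the power gap is what covariate adjustment would give any unadjusted two-group comparison. Both parts stand. A reader might infer that ignoring the matching makes the tests wrong, or that a matched-pair test is required. The documents support neither reading: the matching is of distributions, the groups are unequal, and no pairs exist.

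Four further points stand in part.
- R² is not in the documents, and at R² = 0 nothing is lost. Even then adjustment costs almost nothing, and choosing to match on these factors implies that they were expected to matter.
- The plan states no confidence interval for the group difference, so it cannot be said that planned intervals are too wide. The inflation applies to the standard error inside the tests.
- The planned multiplicity correction means that 0.05 is not the working threshold. This changes the figures but does not remove the gap: at an illustrative 0.01 and R² = 0.3, power is about 34% against 53%.
- Classical risk factors were matched too, so adjusting for age and sex uses only part of the matching. Section 2 does not name the matched factors, and each one added would cost further degrees of freedom.

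The comparisons are also not one of the two stated aims, which limits how much rests on them.

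**Conclusion.** The point holds as a matter of efficiency and clarity, not validity. If age and sex predict the vascular measures and balance is close, a nominal 5% test at each examination has a true type I error of about 4% at R² = 0.1, 2–3% at 0.3 and about 1% at 0.5. Against an adjusted analysis it gives up about 4, 13 and 23 points of power for a 0.5 SD difference at 40 against 42. All of this rests on the assumed R², the assumed difference and an uncorrected two-sided 0.05.

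A reader might go further and conclude that real ET–control differences are missed. The documents do not support that: with R² and the true difference unknown, such differences may be missed, and the loss could be nil. Nor is the power loss a consequence of the matching; only the conservatism is. Separately, the description of the t-test as both paired and for independent samples contradicts itself and needs correcting whatever R² is.

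**What to change.** In section 7:

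1. Delete *paired* from the description of the t-test, and state that matching was at group level with no individual pairs.
2. Compare continuous vascular measures at each examination by linear regression with group, age and sex as terms, transforming the outcome where needed. Report the adjusted difference with its 95% confidence interval, and keep the planned multiplicity correction.
3. Keep the two-sample tests as unadjusted support.
4. Optionally, analyse the plaque and Agatston scores with an ordinal model adjusted for age and sex. Its odds ratio is conditional on the covariates and the standard-error formula above does not carry over to it, so no gain of the size shown should be claimed for it.

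The cost is a change of wording. Age and sex are already held for everyone. The model uses two more degrees of freedom (80 to 78 at the first examination, 72 to 70 at the second if 36 and 38 attend) and assumes a linear effect of age on the chosen scale, which should be checked.

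### Section 7 names a t-test that is both paired and for independent samples; only the unpaired test fits the two groups, and the chi-square rule for discrete variables ignores the order of the 0-6 plaque score

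*Combined protocol and SAP*

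**What the plan says.** Section 7 (Statistical Analysis) sets one rule for comparing patients with controls at the first and at the second examination. It assigns tests by type of variable:

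- Discrete variables go to chi-square.
- Normally distributed continuous variables are tested "for normally distributed continuous variables by the paired Student's t-test for independent samples".
- Non-normal continuous variables go to Mann-Whitney, again described as for independent samples.

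The threshold follows: "P-values of < 0.05 will be considered significant with a correction for multiple comparisons". The correction is not named.

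Section 2 describes the groups. Patients come from a hematology database; controls are hospital employees and their relatives. On matching it says "The groups have been matched for age and sex distribution and classical risk factors for cardiovascular disease", and the inclusion criteria for controls add "matching the patients in age and sex". Forty patients (14 men, 26 women) attended the first examination. For controls: "Forty two control subjects (16 male and 26 female) participated in the first examination". For the second examination, of the patients "36 (12 male and 24 female) of them are expected to participate also in 2018-19", and of the controls "at least 38 (14 male and 24 female) subjects are expected to participate in the second examination".

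Section 4.1 defines the carotid plaque score as a count of affected segments, from 0 to 6. Section 7 does not mention it by name.

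**The concern.** The test name contradicts itself. A paired t-test analyzes within-pair differences and needs each patient tied to one control. A test for independent samples compares two group means and needs no such link. The two use different standard errors and different degrees of freedom.

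An analyst who followed the word paired would have to discard at least two controls at each examination and decide who is paired with whom, with no rule for either step. The same analyst would then use an unpaired test (Mann-Whitney) for the non-normal variables of the same comparison. A result close to the significance threshold could turn on the pairing chosen.

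The second part concerns the plaque score. It is discrete, so the literal rule gives chi-square. That test treats scores of 0, 1, 2 and so on as unordered labels and spreads about 80 people over up to 14 cells.

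**Working it through.** The documents give no effect size, SD, power or sample-size calculation, so there is no stated figure to reproduce. Effect sizes, correlations, score distributions and the Bonferroni divisor below are assumptions.

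**1. Can the groups be paired?** (counts from Section 2)

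| | Patients | Controls | Surplus controls |
|---|---|---|---|
| First examination | 14 + 26 = 40 | 16 + 26 = 42 | 2 |
| Second examination (expected) | 12 + 24 = 36 | 14 + 24 = 38 or more | at least 2 |

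The surplus is among men (14 against 16; 12 against 14), so complete same-sex pairing of everyone is impossible. Unequal numbers alone would not rule out pairing a subset. The decisive fact is that Section 2 describes matching of distributions and nowhere defines individual pairs.

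**2. What would the paired reading change?** Assume a difference d = 0.62 SD, two-sided 0.05, 40 against 42. Power is taken from the noncentral t distribution.

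- Unpaired: noncentrality = d / √(1/40 + 1/42) = 0.62 / 0.2209 = 2.81; df = 40 + 42 − 2 = 80; critical t = 1.990; power 79.2%.
- Paired, 40 pairs, within-pair correlation ρ: noncentrality = d√40 / √(2(1 − ρ)); df = 39; critical t = 2.023. At ρ = 0 this is 0.62 × 6.325 / 1.414 = 2.77; power 77.2%.

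Simulation (40,000 normal data sets per setting) agrees. At ρ = 0, type I error is 4.9% for both tests, and power is 79.1% unpaired and 76.9% paired. The two tests reach different conclusions in 2.0% of data sets under no difference and 5.6% at 0.62 SD. At 36 against 38, simulated power is 75.1% unpaired and 72.4% paired.

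The unnamed multiplicity correction does not change the picture. With an assumed Bonferroni 0.05/7 (seven vascular measures), power at 40 against 42 and ρ = 0 is 52% unpaired and 48% paired.

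The ordering reverses if pairs are correlated. At an assumed ρ of 0.1, 0.25 and 0.5, paired power is 81%, 88% and 97%, against 80%, 82% and 87% unpaired (simulated). The unpaired test's type I error then falls to 3.9%, 2.5% and 0.7%, so it is conservative.

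Near the threshold the choice of pairs does matter. Where the unpaired p is exactly 0.05, 39% of random sex-matched pairings give p below 0.05, and 95% of the paired p-values lie between 0.017 and 0.119. These pairings ignore age, so they only illustrate the dependence.

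**3. Plaque score: chi-square against Mann-Whitney.** Assumed latent shift 0.66 SD, 40 against 42, unadjusted 0.05, 20,000 simulated data sets per setting:

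| Assumed scores | Chi-square power | Mann-Whitney power | Gap (points) |
|---|---|---|---|
| 0-6, evenly spread | 50.2% | 80.2% | 30.0 |
| 0-6, 70% zeros | 38.5% | 71.3% | 32.8 |
| 0-6, 85% zeros, thin tail | 23.8% | 59.6% | 35.8 |
| 0-2 only, 80/12/8% | 53.3% | 63.9% | 10.6 |
| 0-2 only, 60/25/15% | 63.9% | 73.4% | 9.5 |

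With no true difference, chi-square rejects in 0.9% to 4.9% of data sets and Mann-Whitney in 4.6% to 5.1%, so neither inflates error.

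Sparse cells follow directly. With 85% zeros, 0.15 × 40 = 6 patients are expected over six non-zero scores, an average of 1 per cell. With 60% zeros it is 0.40 × 40 = 16, or about 2.7 per cell.

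**The case against.** The strongest reply is that this is a one-word slip with one workable reading. The same phrase says the samples are independent, the Mann-Whitney clause repeats it, and a paired test cannot be run on all 40 and 42 subjects. That stands. A reader might infer that the rule cannot be carried out at all, or that the group comparisons would be invalid. The documents do not support either: the unpaired reading is available, and even arbitrary pairing leaves type I error near 5%.

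A reader might also infer that the study's main conclusions are at risk. Section 1 gives two aims, the difference in 4-year change and the correlation with allele burden. Each has its own analysis sentence in Section 7. The sentence at issue serves neither.

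On the plaque score, it is tempting to say that no test is named. That is not accurate. Section 7 assigns tests by type of variable, the score is discrete, and chi-square is named for discrete variables. What remains is that this test ignores order. One could argue that the normality check on all data sets opens a route to Mann-Whitney, but Section 7 limits that test to continuous variables, so the support is thin.

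Finally, the plaque power figures are not evidence about this cohort. The gap moves from about 10 to 36 points with the assumed distribution. Section 2 excludes clinical disease but says nothing about the distribution of subclinical plaque. This objection stands, and the figures show direction only.

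**Conclusion.** The point holds as a wording error in an operative analysis rule, with low severity. Confidence is high that the two terms exclude each other and that the unpaired test is the one that fits, since no pairs are defined. The consequence of the paired reading is small: about 2 percentage points of power at 40 against 42, assuming 0.62 SD, two-sided 0.05 and zero within-pair correlation, plus dependence on an undefined pairing for results near the threshold. Correlated pairs would favor a paired test, but the documents give no pairs from which to take that gain.

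The secondary point holds with medium confidence because it rests on a literal reading of the discrete rule. Chi-square would waste the ordering of the plaque score. The loss of about 10 to 36 points of power is illustrative, and the error is toward missed differences.

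**What to change.** In the first testing sentence of Section 7, delete the word paired, so that the rule reads as the unpaired two-sample t-test, and say whether the Student or the Welch form is used. Add that the 0-6 carotid plaque score is compared by the Mann-Whitney test, and keep chi-square for nominal variables. Another ordinal method, such as a trend test, would also respect the order; what matters is that one is named in advance.

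The cost is an edit to one sentence of the SAP. Data collection, sample size and the analyses of the two aims are unaffected.
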